##### **2. Mood disorders are common exemplars for complex patients at high risk in need of CCMs.**

Mood disorders (depression and bipolar disorder) are chronic illnesses associated with substantial social dysfunction (23) and rank in the top ten causes of disability worldwide (24). National studies of the U.S. population estimate the lifetime prevalence for bipolar spectrum disorders as 6.4% (25, 26) and 16.6% for major depressive disorder (27). Medical comorbidity is the rule for mood disorders, in which the majority of patients suffer from at least one co-occurring chronic medical illness (28, 29). Persons with mood disorders die younger, mainly from cardiovascular disease (30-32). Quality of care is suboptimal for both chronic medical (33) and mental (34-41) disorders, underscoring the need for coordinated, comprehensive care. Not

surprisingly, the recently released IOM comparative effectiveness priority list includes among its top-quartile priorities research on comprehensive care coordination for chronic diseases (42). While unipolar depression is more common, patients with bipolar disorder incur the most health care costs of any mental illness (43). Up to 70% of direct treatment costs for mood disorders are generated outside the mental health sector, notably in primary care (44-46). In response to extremely high costs and high disease burden associated with mood disorders, Aetna has partnered with us to develop and implement care management methods for this group.

### **3. Health plan-level cross-diagnosis CCMs can address gaps in quality & outcomes for mood disorders**

To date CCMs have not been implemented across mood disorder diagnoses (depression or bipolar disorder), nor have they simultaneously addressed medical and psychiatric outcomes in this group. Given these clear public health deficits, there is a need for adaptation and greater reach of care management strategies beyond single diagnoses. The current state-of-the-science indicates that research efforts should focus more on cross-diagnoses models such as the one proposed in this study as well as issues of spread and sustainability. CCMs have been found to be effective in reducing symptom burden and improving health-related quality of life for depression (3, 47-49) and bipolar disorder (7, 8, 50-53) in separate studies and are now recommended in practice guidelines (54, 55). Our preliminary study of a cross-diagnosis CCM for mood disorders also demonstrated improved outcomes (**Section C**). Moreover, long-term CCM treatment for mood disorders can be cost-neutral (51), and effective among patients with co-occurring substance use disorders (56).

Thus adapting CCMs for this population will require population or health plan level intervention. Moving to plan level care management requires primary reliance on remote rather than clinic-based methods, such as telephone contacts with patients and providers. We have identified 14 reports of 10 trials of telephone care management for depression but none for bipolar disorder (2). These studies recommend a combination of rapport-building telephone care manager-patient contacts with tailored health IT modalities (e.g., web-based self-management, EMRs) (57-69). Several initiatives by our study team also hold promise in a health plan-level implementation of the CCM (**Section C**), notably a telehealth program for bipolar disorder and a web-based, tailored medical care management program for mood disorders (40, (70).

## **B. Innovation**

[figure not shown]
**1. To date this is the first study to implement CCMs in solo or small practices, where many patients with mood disorders are seen:** CCMs have mostly been implemented at the facility level, and primarily developed for and adopted by larger healthcare organizations. However, 50-70% of Americans with mood disorders are managed by commercial insurance plans such as Aetna. Aetna is one of the largest health plans in the U.S., and among its enrollees >90% were seen in solo or small practices (12). This study also complements ongoing efforts in the public sector to implement CCMs through medical home models (10).

**2. Translating CCMs to health plan level models is essential for maximal generalizability:** Plan-level CCMs have rarely been tested in rigorous RCTs (31). A focused implementation of a cross-diagnosis CCM at the national level has implications for the tailoring of evidence-based programs to smaller and rural settings, personalized health care, and implementation of health IT. As technologies around large databases become more sophisticated and complete, implementation programs that successfully apply these rich resources to helping vulnerable populations will serve as important milestones in the nation's transition to a more public health model of care. By focusing on measurement dimensions of the Berwick Triple Aim (care, health, and cost), study findings are potentially generalizable across complex patient populations (71).

**3. Implement CCM using an established strategy to address organization, financing (Figure 1):** We will apply a state of the art framework to implement the CCM across Aetna nationally. Developed by study investigators, the Replicating Effective Programs (**REP**) implementation framework has been used to facilitate the uptake of mood disorder CCMs in prior studies (R01 MH 79994) (72, 73). A variety of implementation frameworks and supporting theories exist (74-78), with relative advantage conferred on those that are (a) theory-based, (b) highly specified operationally, and (c) widely used in relevant contexts. REP is based on the Centers for Disease Control and Prevention's Research Practice Framework (76, 77, 79). Based on Social

Learning Theory (80) and Rogers' diffusion model (81), REP is highly specified operationally into three components that are directly applied to the CCM: Packaging (i.e., translation of CCM materials into user-friendly language), Training, and ongoing facilitated Technical Assistance to address barriers to uptake.

**Figure 1: Enhanced Replicating Effective Programs (REP) to Facilitate Implementation of CCMs**

**Enhanced REP:** In a recent implementation of REP (R01 MH79994), community-based administrators and providers made specific recommendations to the Technical Assistance component that would help develop a **business case** for the CCM based on organizational as well as financial incentives (73). This **Enhanced REP** framework includes ongoing assessment of organizational barriers or facilitators to implementation (11, 82-87) based on the **Organizational Transformation Model- OTM** (88) that assesses both context as well as organizational change factors that might influence implementation. The OTM assessment (72) measures organizational processes found to be associated with improved quality (89), including the practice's readiness to implement new programs (e.g., CCM), leadership commitment, degree to which frontline providers are involved in the operationalization of a new program, and alignment of new program goals with existing priorities and day-to-day processes. Enhanced REP emphasizes dissemination of data to health plan leaders and other stakeholders, and aligning CCM components with reimbursement strategies that may inform the implementation of emerging initiatives including accountable care organizations.

4. This proposal represents a true private-public partnership in light of other AHRQ initiatives (90). Community-based providers involved in our previous studies (R01 MH74509, MH79994) have strongly emphasized the need for CCMs across mood disorders from smaller practices (73). Aetna will provide all care management infrastructure, data, and staff while federal research funds are limited to support of training and evaluation. All products developed from this project will be made available in the public domain based on AHRQ guidelines. Finally, this R18 also addresses unanswered questions raised by a recent AHRQ report on setting a National Agenda for Research in Collaborative Care (2).

**IV. Preliminary Studies:**

Our preliminary studies, including a national study of care management in Aetna and implementation of a cross-diagnosis CCM across the National Network of Depression Centers demonstrate our collective expertise in development and implementation of mood disorder CCMs to improve outcomes across a wide variety of practices, and support the readiness of the mood CCM for a plan-level RCT.

**C.1. Mood disorders in Aetna: Identifying and addressing the need in solo/small practices.** Aetna Inc. is the fifth largest healthcare insurer in the country, providing benefits through employers in all 50 states, with products and services targeted specifically to small, mid-sized and large multi-site national employers. Aetna Behavioral Health serves approximately 12 million covered lives, with 244,971 providers across 157,523 practices filing claims in the past year. Thus while this specific RCT is sited in a single health plan, Aetna has the size and diversity sufficient to represent a wide range of commercially funded care for mood disorders in the US. Aetna has had a longstanding and stable commitment to implementing disease management for high-prevalence, high-cost mental health conditions, as well as a track record of NIH-funded research (e.g.,

1R01DA029716; 1R01DA026414). Aetna’s commitment to sustaining and expanding mental health care management—and the mood disorders CCM in particular—is underscored in the letters from both [name] and Aetna’s in-kind contribution outlined in the Budget Justification.

**C.2. Most Aetna beneficiaries receive care for bipolar disorder from small or solo practices.** Using all Aetna Behavioral Health claims data from 2009, we determined practice size based on number of participating providers linked to the same tax identification number. Unlike the situation for primary care and multi-specialty groups (19, 20, 91), care for bipolar disorder is predominantly provided in small behavioral health practices, with the vast majority of individuals with bipolar disorder treated in solo practices (Table 1). Further, among Aetna patients with bipolar disorder from solo or small practices, **23% (N=2785) were hospitalized** in the past year. This distribution convinced us that it is critical to focus the study on smaller or solo practices in order to truly reach a vulnerable population who to date may not have access to effective care management.

**Table 1: Profile of Aetna Enrollees with Bipolar Disorder by Practice Size**

Practice Size (# Licensed Independent Providers)	# Behavioral Health Practices (%)	# Psychiatrists (%)	# Patients Treated for Bipolar Disorder Seen in Given Practice Venue Size (%)**	Avg. Bipolar Patient Census
Single Independent Psychiatrist	20,318 (84.1%)	20,318 (45.7%)	20,203 (94.4%)	3.5
Single Psychiatrist Registered as Group*	1,250 (5.2%)	1,250 (2.8%)	111 (0.5%)	1.3
Group Practice with 2-3 Psychiatrists	967 (4.0%)	4,428 (10.0%)	207 (1.0%)	2.3
Group Practice with 4-10 Psychiatrists	1,029 (4.3%)	6,875 (15.4%)	329 (1.5%)	2.0
Group Practice with 11-20 Psychiatrists	380 (1.6%)	5,089(11.4%)	225 (1.1%)	2.4
Group Practice with 21-100 Psychiatrists	214 (0.9%)	5,645(12.7%)	318 (1.5%)	4.5
Group Practice with >100 Psychiatrists	14 (0.1%)	894(2.0%)	18 (0.1%)	18.0
Total Number of Practices	24,172 (100.0%)	44,449 (100.0%)	21,411 (100.0%)	--

\*Individual providers could register with Aetna either as an independent practitioner or as a group at their own discretion.  
 \*\*Analysis of 20,933 unique patients treated for bipolar disorder; 1,675 (0.8%) received care in >1 venue.

greater reduction in costs among CM vs. EC participants (Cohen's D=0.21) (Table 2). Importantly, outpatient visits were not decreased in the control group, indicating that the protocol did not disrupt usual care. Moreover, care managers identified 4 out of 457 patients who had suicidal ideation and, through established protocols, alerted the provider and arranged emergency evaluation; and no suicide attempts occurred during the study. This study indicates that: (a) participants can be successfully enrolled into a plan-level care manager RCT; (b) care management can be successfully implemented with participants across time zones from a national call center; and (c) claims data suggest that care management may have had beneficial effects.

**Table 2: Changes in Costs among Aetna Patients Randomized to CM or EC: National Data**

	Care Management (mean \$±SD)			Educational Control (mean \$±SD)		
	6 Mos Pre	6 Mos Post	Difference	6 Mos Pre	6 Mos Post	Difference
Aetna BH \$/member	5,210±8,370	934±2,210	-4,277±7,926	6,048±6,347	3,492±7,621	-2,556±8,461

**C.4. NNDC Multisite mood CCM implemented by existing providers improves outcomes.** In a randomized controlled pilot study we determined the effectiveness of a cross-diagnosis mood CCM compared to education control in a cohort of outpatients with unipolar depression or bipolar disorder from four sites affiliated with the National Network of Depression Centers (NNDC). NNDC is the nation's largest network of academic and community-affiliated mental health and primary care clinics representing a diverse practice size and patient population. Existing care managers at four NNDC sites (Ann Arbor, Palo Alto, San Francisco, Denver) were trained by study investigators to implement the CCM using Enhanced REP. Sixty patients (mean age=46, 40% bipolar diagnosis, 73% female, 17% African-American) with mood disorders were identified using chart reviews and randomized to CCM or usual care. CCM included phone-based self-management and care management as well as guideline dissemination to providers. Repeated measures analyses comparing changes in 3 and 6-month outcomes revealed clinically significant probability of depression remission (>50% PHQ-9 score reduction and <=9 on PHQ-9 in 6 months): 50.1% for CCM vs. 19.0% for EC group (OR=9.4, p=.04) and improved well-being (positive symptoms based on the Internal State Scale-ISS - Cohen's D=.36).

**Table 3: 6-Month Outcomes Comparing CCM vs Education Control (EC): Repeated Measures Analysis**

Outcomes(N=60)	CCM (N=29)			EC (N=31)			Repeated measures results		
	Baseline	3-mon	6-mon	Baseline	3-mon	6-mon	Beta	T(p)	Effect(D)
PHQ-9	13.7 (7.5)	9.3 (6.5)	6.3 (4.2)	16.8 (6.5)	14.0 (6.6)	11.9 (6.8)	-1.24	-1.37(.17)	-.22
50% drop: PHQ-9 and PHQ-9 <=9			50.0%			19.0%	OR=9.4; Chi-sq= 4.18; p=.04		
ISS-Wellbeing	13.0 (7.9)	15.8 (8.3)	20.4 (7.8)	10.2 (6.9)	12.5 (7.8)	12.4 (8.1)	2.22	2.35(.02)	.36

## V. Methodology

**Overview.** We will conduct an RCT of the **CCM** for mood disorders vs. an educational mailing control (**EC**). The population of interest will be Aetna adult enrollees and family members (beneficiaries) across the country hospitalized for an episode of unipolar depression or bipolar disorder and belonging to a solo (i.e., single provider) or small practice (2-3 providers). Patients will be randomized to CCM or EC. The CCM will be implemented using Enhanced REP (76, 77, 79) as we have in prior studies (72, 73, 76). CCM care management will be fully remote from practice venues and patients, implemented by Aetna care managers. CCM and EC strategies represent add-ons to ongoing practice, which will not otherwise be altered. Main outcomes include mood symptoms (e.g., PHQ-9) and health-related quality of life (SF-12), accounting for nesting of patients within practices.

**C.5.b. Sample recruitment, eligibility, enrollment (Figure 2).** The following steps will be taken to enroll participants, provide informed consent, and randomize them. Participant recruitment and treatment will utilize existing Aetna resources.

[figure not shown]
1. Aetna care managers will recruit participants by first screening them based on near-real time information of recent hospitalizations (as with the pilot study). At hospitalization, Aetna is notified for (pre)authorization, typically before or within 48 hours of admission. Care managers will be notified about patient hospitalizations via the Aetna care management registry, eTUMS (Section C.5.c) and will contact the potential participant by phone as in the pilot study (Section C.4.a). Care managers will screen for eligibility and obtain informed consent and authorization to release information to the research team and to coordinate care with their providers. This will be done over the telephone after verbally explaining the protocol, risks, benefits, and safety measures via written script based on previous RCTs (92, 93). Because patients have not been randomized at this point, Aetna care managers will be blind to treatment assignment at baseline.

2. Patient inclusion criteria as determined by the care managers include:

- a. Adult patients age 21 years or older from the contiguous United States (lower 48 states)
- b. Currently covered by Aetna’s HMO or preferred provider products (for whom Aetna provides mental and medical inpatient, outpatient, and pharmacy benefits) for at least 6 months
- c. Recent (past 6-month) hospitalization for an acute psychiatric or partial hospital unit with a manic or depressive episode and confirmation of mood disorder diagnosis at discharge (52).
- d. Ability to speak and read English and provide informed consent

4. The research associate (RA), who will be external to Aetna to maintain separation of care management and program evaluation, and will be blinded to randomization assignment. (S)he will be trained by Aetna on their well-established call implementation program across time zones (**Section C.5.c**) and by study investigators in human subjects risk reduction procedures used in prior studies (8, 50) that will minimize risk while not compromising study internal validity (8). The initial assessment (described below) will include a brief survey baseline factors, including demographics, employment, whether they were the Aetna enrollee or a family member, and primary

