**Figure 2: Implementation of Mood CCM across Health Plan, Practices, and Patients**

clinician who treats their mood disorder (i.e., prescribes psychotropic medications). Comorbidities will be ascertained from Aetna eTUMS chart reviews conducted by the RAs.

program evaluation, and will be blinded to randomization assignment. (S)he will be trained by Aetna on their well-established call implementation program across time zones (**Section C.5.c**) and by study investigators in human subjects risk reduction procedures used in prior studies (8, 50) that will minimize risk while not compromising study internal validity (8). The initial assessment (described below) will include a brief survey baseline factors, including demographics, employment, whether they were the Aetna enrollee or a family member, and primary

**C.5.c. Existing Aetna Infrastructure Used in this Study.** The following components are of specific relevance:

1. The registry/database consists of four main components and will be used to identify potentially eligible patients as well as ascertain utilization and other outcomes data (see variable descriptions below). The Electronic Total Utilization Management System (**eTUMS**), a proprietary care management tool is populated by

claims data augmented by customizable care manager input; major claims events, such as hospitalization, result in automatic care manager notification. The **pharmacy claims database** accrues prescription claims daily, including drug and dose, and is downloaded to eTUMS on a weekly basis. **Laboratory claims data** are similarly downloaded on a monthly basis; laboratory reports contain the name of the test, while reports from larger laboratories also provide results. Thus these registries will provide the data necessary to measure guideline-concordant care (e.g., non-filling of mood disorder prescriptions, non-completion of cardiometabolic laboratory tests). The fourth component, **Aetna claims data**, includes use and cost data for Aim 3.

**2. The Aetna care management infrastructure is substantial and stable.** The masters level Aetna care managers who participated in the pilot will serve as the CCM care managers. They have a minimum of 5 years of care management experience with Aetna, providing short-term or ongoing care management for an average of 300 beneficiaries per year across multiple time zones and patient schedules.

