**Aim 3: Utilization, costs, CEA, and business case:** Primary utilization measures of interest, including outpatient services, inpatient (including length of stay), and ER use, and health care costs will be ascertained from Aetna eTUMS electronic record reviews using a standard assessment tool (125). Cost data will be estimated for each inpatient, ER, and outpatient visit using Current Procedural Terminology (CPT) codes. A relative value unit (RVU) weight will allow for the use of the Medicare Fee Schedule to calculate a standardized cost for each service. Costs incurred in different years will be discounted at an annual rate of 3% and adjusted for inflation and discounted to the baseline (first) year of the study. Other costs incurred by the participants including medications, visit co-pays, transportation, and time involved in the CCM will be ascertained from the

patient survey. CCM cost data will be estimated using a time-motion survey developed by study investigators (R01 MH 79994) administered monthly to the CMs and quarterly to providers over a 2-year period, which ascertains time spent on CCM activities, including self-management, phone contacts, and documentation.

**C.5.g. Analyses.** General approach: The principal analyses will be for the primary hypotheses. An intent-to-treat analysis will be performed for all analyses. Bivariate baseline analyses will first be conducted to see if randomization was successful by comparing patient demographics and clinical characteristics (e.g., mental health diagnoses) between randomization groups. If there is a lack of equal distribution across groups, these variables will be added as covariates to analyses or propensity scoring will be used. Baseline characteristics will be compared among those enrolled but dropped out over time to those who remained in the study. Our unit of analysis for patient-level outcomes will be patients nested within practices with an indicator for non-solo practice provider sites (126, 127) and an indicator for patients diagnosis (bipolar vs. unipolar depression).

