Missing Data: We attained subject retention of 80% over a three-year follow-up in one study (50, 51), and recent 1-year data (MH0745409) indicate 90% retention. Extent and pattern of missingness will be examined for outcome variables as well as for baseline covariates. We expect missingness to be completely at random or at random, in which case the proposed analytical methods will give unbiased estimates of treatment comparison. We will examine how sensitive our conclusions are to potential non-ignorable missingness using a pattern mixture model that will allow us to either model the observed pattern of missingness or change the imputations to represent the likely differences in conditional distributions between observed and missing data (128, 129). For the latter, we will combine the results from each imputed data using Rubin's rules (130).

**Aim 1 primary outcomes (H1a: symptoms, quality of life):** Primary outcomes are continuous, and based on pilot data, are expected to be normally distributed. If a continuous outcome exhibits a significant lack of normality, other options will be considered including data transformation, categorization, and non-parametric analyses. Four linear mixed-effects models accounting for clustering will be run to assess the CCM effects compared to EC on changes in PHQ-9, ISS, and SF-12 PCS and MCS scores over 12-months, adding baseline values of the outcome measure, the effect of CCM, time, and CCM X time interaction.

**Aim 1 secondary analyses:** For guideline concordance and hospitalization, we will compare the likelihood of receiving the guideline-concordant treatment over 12 months (Table 5) as well as the likelihood of an ambulatory care sensitive admission using a generalized linear mixed-effects model (GLM) with logit link. Similar to our primary hypotheses, linear mixed-effects models will be conducted to determine the effect of CCM vs. EC on changes in the Work and Social Adjustment Scale.

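### The primary models could adjust for time since index discharge, because criterion c lets patients enter up to 6 months after an admission; the likely gain in precision is small

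*Combined protocol and SAP*

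**What the plan says.** **Eligibility and timing (C.5.b).** Criterion c requires a "Recent (past 6-month) hospitalization for an acute psychiatric or partial hospital unit with a manic or depressive episode" together with "confirmation of mood disorder diagnosis at discharge". Care managers recruit by "first screening them based on near-real time information of recent hospitalizations", and "Aetna is notified for (pre)authorization, typically before or within 48 hours of admission". Six months is the outer limit. No distribution of entry times is given.

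**Primary models (C.5.g, Aim 1 primary outcomes).** Four linear mixed models, for PHQ-9, ISS, PCS and MCS, account for clustering and are built by "adding baseline values of the outcome measure, the effect of CCM, time, and CCM X time interaction". The general approach in the same section adds a non-solo-practice indicator and "an indicator for patients diagnosis (bipolar vs. unipolar depression". Other baseline variables enter only if the arms turn out to be unequal. Neither time since discharge nor polarity of the index episode is named as a covariate, and neither appears in the exploratory Aim 2 list.

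**Data held (C.5.c).** eTUMS is fed by claims, and "major claims events, such as hospitalization, result in automatic care manager notification".

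**The concern.** The baseline survey may fall anywhere from days to nearly six months after the index stay. Soon after a depressive admission, a PHQ-9 score may carry acute illness that will fade. The same score at five months is probably closer to the patient's usual level. A model with one common baseline slope treats the two scores alike, so the transient part acts like measurement error: it weakens the baseline adjustment and leaves explainable variance in the residual. Time since discharge tells the model how much of the score is likely to be transient, so it can carry information even when the baseline score is already in the model.

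Polarity of the index admission works in a similar way, but only within bipolar disorder. Unipolar patients have depressive episodes, and the planned diagnosis indicator already separates them from bipolar patients.

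The rule that adds covariates after an imbalance would not reliably bring in time since discharge. A prognostic covariate improves precision even when the arms are perfectly balanced. What is at stake is the standard error of the CCM contrast, not its validity.

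**Working it through.** **1. Reproduce the plan's sample size (C.5.i).** Inputs are D = 0.36, two-sided 0.05, 90% power, ICC 0.05 and 2 patients per practice.
- Independent patients per arm: 2 × ((1.960 + 1.282)/0.36)² = 162.2, rounded up to 163.
- Design effect: 1 + (2 − 1) × 0.05 = 1.05.
- 163 × 1.05 = 171.2, so 86 practices of 2, or 172 per arm and 344 in total. This matches the plan.

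The match is to the number before dropout. With 20% loss, 172 × 0.8 = 137.6 per arm remain. This shortfall is a separate matter and serves here only as the starting point.

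**2. Power as a function of residual variance removed.** If added covariates remove a share R² of the residual variance, power = Φ(0.36 × √(n / (2 × 1.05 × (1 − R²))) − 1.96).

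| R² | Power, n = 172 | Power, n = 137.6 |
|---|---|---|
| 0 | 90.3% | 83.0% |
| 1% | 90.6% | 83.4% |
| 2% | 90.8% | 83.7% |
| 3% | 91.1% | 84.1% |
| 4% | 91.4% | 84.5% |
| 5% | 91.7% | 84.9% |

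**3. Range for R².** The documents give no value, so this step rests on assumptions. A large-sample simulation of a single 12-month PHQ-9 regression used:
- a usual level of 9 (SD 4.5)
- a baseline equal to level + excess × exp(−t/τ) + error (SD 3)
- a 12-month score equal to level + error (SD 4)
- a mean acute excess of 6–8 points, with τ of 1.5–3 months
- 20% manic index episodes and 40% bipolar (the bipolar share is from the 60-patient pilot in C.4).

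The comparator model already contained baseline score and diagnosis. Results depended on the further assumptions:
- Time, polarity and their product removed about 3–7%, but only if manic admissions carry no PHQ-9 excess and neither excess nor decay varies between patients.
- With those restrictions relaxed, and with lower excess or manic share and early entry also allowed, the same three terms removed about 0.4–4%, and time alone about 0.1–4%.
- At the low end (entry within one month of discharge, 10% manic episodes, mean excess 3–6 points), the three terms removed 0.5–1.0%.

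**4. Polarity beyond diagnosis.** With bipolar share b, manic share q among bipolar patients and a residual difference of d SD, R² = b × q × (1 − q) × d². The low case is 0.4 × 0.3 × 0.7 × 0.2² = 0.3%. The high case is 0.5 × 0.5 × 0.5 × 0.5² = 3.1%. All of b, q and d are assumed.

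**5. Cost in degrees of freedom.** With 2 × 137.6 = 275 completers, each fitted term inflates the variance of the contrast by about 1/275 = 0.4%. Two terms cost 0.7%, and three cost 1.1%.

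**6. Net gain.**
- Upper end, time alone: 4% − 0.4% = 3.6%. Power is Φ(2.968 − 1.960) = 84.3%, a gain of 1.3 points. Before the cost it is 84.5%, a gain of 1.5 points.
- Lower end, time alone: 0.1% − 0.4% = −0.3%. Power is 82.9%, in effect no change.

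The net gain is therefore roughly 0 to 1.5 power points.

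**The case against.** The strongest reply is that nothing here is wrong. In a randomised comparison with linear models, leaving out a prognostic covariate does not bias the treatment contrast. The plan already adjusts for the baseline value of each outcome, diagnosis and practice type, and almost any trial could be told to add one more covariate. That stands, and it limits the point to an optional refinement. It does not dispose of it, because time since discharge follows directly from this trial's own entry window and costs almost nothing to include.

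Second, recruitment works from near-real-time admission notices, so actual entry may cluster soon after discharge. That also stands. The time term would then add little, and a reader should not infer from criterion c alone that acute and recovered patients are in fact mixed in large numbers.

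Third, a reader might infer that discharge date and polarity are both on file for every randomised patient because criterion c needs them. The documents support this only in part. A discharge date should be derivable from the claims-fed registry. For polarity, the criterion can be met by either kind of episode, and only a mood disorder diagnosis must be confirmed at discharge; polarity is not documented as a recorded variable.

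Fourth, a reader might infer a gain of 3–7% of residual variance, or 1 to 2.5 power points. That range needs the restrictive assumptions named in step 3 of the check, none of which the documents supply. The calculation also covers only PHQ-9 at 12 months, in a single regression and not the planned mixed model. It shows nothing for ISS, PCS or MCS.

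**Conclusion.** The point holds as a small, cheap gain in precision. Time since index discharge is a plausible prognostic covariate that can be derived from data the trial receives, and the primary models omit it. The validity of the CCM contrast is not affected.

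The size is not determined by the documents. Under assumed ranges it is about 0 to 1.5 power points for PHQ-9, from about 83% with 20% dropout, after allowing for degrees of freedom. It could be negligible if most patients complete baseline soon after discharge. Polarity adds information beyond the diagnosis indicator only among bipolar patients, and only if it is captured. A product of polarity and time is not justified on this evidence.

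**What to change.** In C.5.g, state that the primary models include days from index discharge to the baseline survey as a fixed covariate, whatever the balance between arms, taken from claims or eTUMS. The same sentence should define the index stay where a patient has several, say how a partial-hospital stay still under way at baseline is counted, and fix the functional form (for example linear) before unblinding.

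Add index-episode polarity (manic versus depressive) as a single main effect if it is recorded at screening or derivable from the discharge diagnosis, with a stated category for mixed episodes. Do not add a polarity-by-time product.

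The cost is a short addition to the analysis text and one or two degrees of freedom, plus at most one screening field if polarity is to be used. Enrolment, visits and the treatment contrast being estimated are unchanged.
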